Clinical Pharmacology Study Protocol

[figure not shown]
Drug Substance AZD6140
Study Code D5130C00028
Edition Number 1.0
Date

An Exploratory, Double-Blind, Randomized, Placebo-Controlled, 2-Period Crossover, 3 Cohort Pharmacokinetic/Pharmacodynamic, Single Center Study to Assess the Effect of AZD6140 on Respiratory Parameters in Healthy Subjects, Mild Asthmatics and COPD Patients Age 55 to 75 Years

The following Amendment(s) and Administrative Changes have been made to this protocol since the date of preparation:

Amendment No.	Date of Amendment
_____	_____
_____	_____

Administrative change No.	Date of Administrative Change
_____	_____
_____	_____

ASTRAZENECA PROCEDURES IN CASE OF EMERGENCY

In the case of a medical emergency you may contact the Clinical Study Team Leader. If the Clinical Study Team Leader is not available, contact the Clinical Study Team Physician at the AstraZeneca Research and Development site shown below.

Role in the study	Name	Address and Telephone number
Clinical Study Team Leader		
Clinical Study Team Physician		

For further clarifications regarding:

- Procedures in case of medical emergency see Section 8.2
- Procedures in case of overdose see Section 8.3.
- Procedures in case of pregnancy see Section 8.4 (not applicable)

PROTOCOL SYNOPSIS

An Exploratory, Double Blind, Randomized, Placebo-Controlled, 2-Period Crossover, 3 Cohort Pharmacokinetic/Pharmacodynamic, Single Center Study to Assess the Effect of AZD6140 on Respiratory Parameters in Healthy Subjects, Mild Asthmatics and COPD Patients Age 55 to 75 Years

Investigator

6

Study centre(s), type and number of subjects planned

Approximately 24 subjects (male or female of non-child bearing potential) including 8 healthy volunteers, 8 mild asthmatic patients and 8 mild chronic obstructive pulmonary disease(COPD) patients aged 55 to 75 years, inclusive, will be randomized at a single center.

Study period

Estimated date of first subject enrolled

Estimated date of last subject completed

Phase of development

Clinical Pharmacology (I)

Objectives

The primary objective of the study is to:

- Assess the effect of AZD6140 on respiratory rate and minute ventilation

The secondary objectives of the study are to:

- Assess the effect of AZD6140 on other respiratory parameters;
- Evaluate the pharmacokinetic/pharmacodynamic (PK/PD) relationship between AZD6140/AR-C124910XX concentrations and respiratory parameters in healthy volunteers, mild asthma patients, and mild COPD patients;

- Compare respiratory parameters between the healthy volunteers, mild asthma patients, or COPD patients;
- Compare the pharmacokinetics (PK) of AZD6140 and AR-C124910XX in healthy volunteers, mild asthma patients, or COPD patients.
- Examine the safety and tolerability of AZD6140 in healthy volunteers compared with mild asthma patients or mild COPD patients.

Study design

This will be a randomized, double blind, placebo-controlled, 3 cohort PK/PD, single center study to assess the effect of AZD6140 on respiratory parameters in healthy volunteers, mild asthmatic and COPD patients age 55 to 75 years.

Investigational product, dosage and mode of administration

Each subject will receive each of the following treatments according to the randomization schedule:

Treatment A: A single, oral dose of 450 mg AZD6140 (5 x 90 mg immediate release tablets) will be administered in the AM of Study Day 1; followed by a single, oral dose of 180 mg AZD6140 (2 x 90 mg immediate release tablets) in the PM (12 hours after the first dose); thereafter, 180 mg AZD6140 (2 x 90 mg immediate release tablet) will be administered bid (every 12 hours) on Study Days 2 and 3 and in the AM only on Study Day 4.

Treatment B: A single, oral dose of AZD6140 matching placebo (5 placebo tablets) will be administered in the AM of Study Day 1; followed by a single, oral dose of AZD6140 matching placebo (2 placebo tablets) in the PM (12 hours after the first dose); thereafter, AZD6140 matching placebo (2 placebo tablets) will be administered bid (every 12 hours) on Study Days 2 and 3 and in the AM only on Study Day 4.

Duration of treatment

The duration of subject participation will be up to approximately 45 days, including:

- **Screening period:** within 21 days before Day -1, Period I admission
- **Periods I/II:** will each consist of a 6 day/5 night inpatient stay
- **Washout Period:** at least 7 outpatient days between Study Day 5 of Period I and Study Day 1 of Period II.
- **Follow-up visit:** within 4 to 7 days of last inpatient day of Period II

Each subject will receive 1 dose of 450 mg AZD6140, 6 doses of 180 mg AZD6140 and 7 doses of AZD6140 matching placebo tablets according to the randomization schedule.

Variables

- Pharmacokinetic

The following pharmacokinetic parameters will be assessed:

Day 1: C_{max} , t_{max} , $AUC_{(0-12)}$, for AZD6140 and AR-C124910XX and the metabolite to parent C_{max} and AUC ratios.

Day 4: C_{max} , t_{max} and AUC_{τ} , for AZD6140 and AR-C124910XX, AZD6140 CL/F and the metabolite to parent C_{max} and AUC ratios.

- Pharmacodynamic

Cardiopulmonary exercise test

Minute ventilation

Spirometry (FEV_1 , FVC)

Respiratory Rate

Modified Borg Scale

Bidirectional Dyspnea Index

- Safety

Safety and tolerability will be assessed by collection of adverse events, 12-lead ECG (electrocardiogram), blood pressure, heart rate, physical examination results and laboratory assessments (chemistry, hematology, urinalysis), use of albuterol MDI.

- Genetics

Genetic analysis of the genes that are involved in absorption and disposition of, and response to AZD6140 such as the MDR-1 gene may be performed for those volunteers providing separate informed consent. The genetic samples collected from this study may be pooled with those from other studies involving AZD6140.

- Statistical methods

The respiratory parameters, and changes from baseline, will be summarized at each scheduled time point by treatment and visit for each of the cohorts using descriptive statistics. These will also be supported with graphical displays in order to ease making comparisons.

The pharmacokinetic parameters will also be descriptively summarized at each scheduled time point and treatment for the cohorts. Furthermore, graphical plots of the respiratory parameter and concentration of AZD6140 will also be explored for each of the three cohorts by visit.

Clinical Pharmacology Protocol
Study Code D5130C00028 Edition Number 1.0
Date

Safety data (adverse events, vital signs, 12-lead ECGs, laboratory data, physical examination data) will be summarized at each scheduled time point by treatment for the three cohorts using descriptive statistics.

The results of genetic analysis, if any, will be exploratory and will not be included in the clinical study report of this study.

TABLE OF CONTENTS	PAGE
TITLE PAGE.....	1
PROTOCOL SYNOPSIS.....	3
TABLE OF CONTENTS.....	7
LIST OF ABBREVIATIONS AND DEFINITION OF TERMS.....	12
1. INTRODUCTION.....	15
1.1 Background.....	15
1.2 Rationale.....	16
2. STUDY OBJECTIVES.....	17
2.1 Primary objective.....	17
2.2 Secondary objective(s).....	17
3. STUDY PLAN AND PROCEDURES.....	17
3.1 Overall study design.....	17
3.1.1 Screening/Visit 1.....	18

Outcome variable	A, usually derived, variable specifically defined to be used in the analysis of a study objective
PCP	Phencyclidine
PCRF	Paper Case Report form
PD	Pharmacodynamics
PGx	Pharmacogenetics
PK	Pharmacokinetics
Parameter	A quantity (usually unknown) that characterizes the distribution of a variable in a population of subjects
Principal investigator	A person responsible for the conduct of a clinical study at a study site. Every study center has a principal investigator.
RPM	Revolutions per minute
SAE	Serious adverse event
SaO ₂	Oxygen saturation
SAP	Statistical analyses plan
TBD	To be determined
THC	Tetrahydrocannabinol
t _½	Terminal phase half-life

Abbreviation or special term	Explanation
t_{\max}	Time to reach maximum (peak) concentration
ULN	Upper limit of Normal
Variable	A characteristic or a property of a subject that may vary e.g., from time to time or between subject
V_E	Minute ventilation
VO_2	Oxygen uptake
V_T	Tidal volume
Wcap	Work capacity
WHO	World Health Organization

1. INTRODUCTION

1.1 Background

Adenosine diphosphate (ADP) is an important mediator of platelet activation and aggregation through its binding to at least 2 distinct subtypes of purinoceptor, designated P2Y₁ and P2Y₁₂, found on platelets. Two ADP receptor antagonists, thienopyridine pro-drugs, clopidogrel and ticlopidine have shown clear benefits for the reduction of clinical thromboembolic events in patients with atherosclerosis due to their ability to block the P2Y₁₂-receptor. However, this blockade is irreversible and usually incomplete. In addition, there are some safety concerns for the use of ticlopidine. Therefore, the search continues for agents which can further improve the clinical outcomes of these patients through improved efficacy and/or safety.

AZD6140 is a potent, reversible, P2Y₁₂-receptor antagonist (antiplatelet agent) being developed to reduce thromboembolic events in patients with atherosclerosis. It is orally active and does not require metabolic activation, different from clopidogrel, for which only the metabolites are active. Unlike clopidogrel and ticlopidine, which incompletely block the P2Y₁₂-receptor response in humans, pre-clinical studies indicate that AZD6140 can produce long-lasting and complete inhibition of ADP-induced platelet aggregation *ex vivo* following oral dosing.

Twelve phase I studies conducted primarily in Caucasian subjects and two phase I trials conducted in Japanese and Caucasian subjects have completed dosing as of the end of June 2004. The data from these studies demonstrate a well tolerated safety profile for AZD6140 over the dose range of 0.1 to 600 mg (for periods up to 20 days). There is a positive relationship between the plasma concentration of AZD6140 and the degree of inhibition of platelet aggregation (IPA), with all volunteers achieving a high level of inhibition of 20 µmol ADP-induced aggregation.

Study SC-532-5239 evaluated the safety and tolerability of multiple ascending doses (tablets) of AZD6140 in healthy male and female subjects in Europe. Once and twice daily dosing regimens of AZD6140 with total daily doses ranging from 50 mg to 600 mg administered for 5 days at each dose level (a total duration of 15 or 20 days) were studied, compared with 75 mg clopidogrel. Multiple doses of AZD6140 were well tolerated. The pharmacokinetics (PK) of AZD6140 following multiple oral dosing was approximately linear over 50 mg to 600 mg. Maximum plasma concentrations (C_{max}) were reached within 1.5 to 3 hours after dose intake, and the mean terminal half-life (t_{1/2}) of AZD6140 ranged from 6 to 13 hours. The metabolite area under the plasma concentration-time curve (AUC) and C_{max} were about 35% of the corresponding parameters for AZD6140 and were approximately linear over 50 mg to 600 mg dosing of AZD6140. Greater than 80% inhibition of platelet aggregation was observed at all doses studied. In terms of inhibition of platelet aggregation, twice-daily doses were superior to the equivalent total daily dose given every 24 hours. All total daily doses of AZD6140 above 200 mg were superior to once-daily doses of 75 mg clopidogrel in terms of pharmacodynamics response. In addition, in this study, the effect of food on the PK and PD of AZD6140 was studied in an exploratory way (comparison between the data under fasting

condition on Day 15 and under fed condition on Day 16). Plasma concentrations and AUC values for AZD6140 were slightly higher following administration of AZD6140 under fed condition. There did not appear to be any effect on these for the metabolite. Due to the study design, however, the exact magnitude of the effect of food could not be estimated from these data. There was no obvious effect of food on PD response.

No serious adverse events were observed in the 14 Phase I studies completed to date. Approximately 388 healthy volunteers were entered into these trials, and 337 healthy volunteers received at least 1 dose of AZD6140. The most common adverse events reported to date in the Phase I studies include: increase in liver function tests, tachycardia, orthostatic hypotension, rash, and bleeding events including skin bruising, epistaxis, and gingival bleeding. However, the causal relationship of these adverse events to AZD6140 is uncertain. There were no electrocardiogram (ECG), Holter monitor or vital sign findings of concern during any of the studies.

It is well known that drug response can be affected by genetic variables. In vitro studies have shown that AZD6140 is a substrate of cytochrome P450 enzyme CYP3A and P-glycoprotein, a transmembrane transporter encoded by MDR-1 gene. Functional polymorphisms in the genes encoding both CYP3A and the transporter have been identified and have the potential to impact pharmacokinetics of AZD6140. It is also possible that information on other genes influencing the disposition of and response to AZD6140 will become available in the future. It will therefore be important to consider the possibility of investigating additional genes in the future.

1.2 Rationale

This study is to be conducted to evaluate the respiratory symptoms and physiological parameters that may be associated with the sensation of dyspnea in subjects receiving AZD6140. Dyspnea was reported in association with AZD6140 administration in DISPERSE, a phase IIa study in stable outpatients with documented atherosclerosis, but not healthy volunteers. One pre-clinical study in rats demonstrated an increase in respiratory rate at concentrations of AZD6140 that are clinically relevant. Non-clinical studies have demonstrated that, at relatively high concentrations, AZD6140 has an affinity for the adenosine transporter in erythrocytes. This is a potential mechanism for the observed effect. Adenosine administration has been associated with dyspnea, flushing, and chest discomfort. Dyspnea has also been observed clinically with dipyridamole, which inhibits the erythrocyte adenosine transporter. Respiratory symptoms invoked by adenosine are thought to be due to activation of arterial chemoreceptors. The target population of patients with ACS are likely to include those with asthma and COPD. Therefore healthy volunteers, as well as patients with mild asthma and COPD will be included to assess whether the sensitivity of patients with respiratory disease is greater than in healthy volunteers. The pharmacodynamic effect of AZD6140 on respiratory parameters will be assessed by cardiopulmonary exercise test, respiratory rate, minute ventilation, spirometry (FVC, FEV₁), modified Borg Scale¹, and Bidirectional Dyspnea Index². Pharmacokinetics of AZD6140 and its active metabolite AR-C124910XX will be assessed to correlate the PD effect on respiratory parameters with plasma concentrations of AZD6140 and AR-C124910XX.

A retrospective analysis of the polymorphisms of genes that are important to the absorption and disposition of, and response to AZD6140 may be performed. The genetic data from this study may be pooled with genetic results from other studies on AZD6140 to generate hypotheses to be tested in future studies. The results of the genetic analysis, if any, will not form part of the clinical study report.

2. STUDY OBJECTIVES

2.1 Primary objective

The primary objective of the study is to:

- Assess the effect of AZD6140 on respiratory rate and minute ventilation.

2.2 Secondary objective(s)

The secondary objectives of the study are to:

- Assess the effect of AZD6140 on other respiratory parameters;
- Evaluate the pharmacokinetic/pharmacodynamic (PK/PD) relationship between AZD6140/AR-C124910XX concentrations and respiratory parameters in healthy volunteers, mild asthma patients, and mild COPD patients;
- Compare respiratory parameters between the healthy volunteers, mild asthma patients, or COPD patients;
- Compare PK of AZD6140 and AR-C124910XX in healthy volunteers, mild asthma patients, or COPD patients.
- Examine the safety and tolerability of AZD6140 in healthy volunteers compared with mild asthma patients, or mild COPD patients.

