All healthy volunteers (Cohort A) will be dosed and evaluated initially. *A blinded review of the safety data (adverse events, spirometry, respiratory rate) for the healthy volunteers will be performed by the sponsor at the completion of Cohort A to assess any issues for safety prior to dosing Cohorts B and C. The sponsor will give written approval to proceed with dosing of the next 2 cohorts.* Dosing of Cohorts B and C can be completed simultaneously.

3.1.1 Screening/Visit 1

In order to establish eligibility to participate in the study, potential subjects will undergo all screening procedures and assessments within 21 days before Day 1 of Period I, after giving written informed consent. Please refer to Table 1 and Section 4.1.1 for procedures and assessments to be completed at the screening visit.

3.1.2 Period I/Visit 2

Each day will be based on a 24-hour clock beginning at midnight (00:00).

Subjects will be admitted to the study center on Day –1 and will reside in the study center from Study Day-1 until completion of all protocol-driven procedures and assessments on Study Day 5 of Period I. The assessments on Study Day –1 of Period I, will reconfirm the subject eligibility to participate in the study. The results of the assessments must be confirmed before the subject is randomized and receives study medication on Day 1 of Period I.

All subjects will be required to begin an overnight fast on the evening of Study Day –1. On Study Day 1 of Period I, each volunteer will receive one of the following treatments according to the randomization schedule:

Treatment A: A single, oral dose of 450 mg AZD6140 (5 x 90 mg immediate release tablets) will be administered in the AM of Study Day 1; followed by a single, oral dose of 180 mg AZD6140 (2 x 90 mg immediate release tablet) in the PM (12 hours after the first dose); thereafter, 180 mg AZD6140 (2 x 90 mg immediate release tablet) will be administered bid (every 12 hours) on Study Days 2 and 3 and in the AM only on Study Day 4.

Treatment B: A single, oral dose of AZD6140 matching placebo (5 placebo tablets) will be administered in the AM of Study Day 1; followed by a single, oral dose of AZD6140 matching placebo (2 placebo tablets) in the PM (12 hours after the first dose); thereafter, AZD6140 matching placebo(2 placebo tablets) will be administered bid (every 12 hours) on Study Days 2 and 3 and in the AM only on Study Day 4.

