This will be a double-blind, randomized, placebo-controlled, 2-period crossover, 3 cohort, pharmacodynamic study. Healthy volunteers are included as well as patient population (mild asthma and COPD patients) so that qualification of the differences in physiologic response and subjective experience of dyspnea can be compared to a healthy population.

Asthma and COPD patients are included primarily to ascertain if the physiologic response differs from healthy volunteers as this observation was only observed in a patient population and not in healthy volunteers in Phase I studies. Additionally, examining any dyspnea effects in COPD and asthma patients as compared to healthy volunteers will help to establish safety parameters. Healthy volunteers will be studied first to increase safety. The age range encompasses that of the Phase II study where dyspnea was first observed. Mild disease patients are chosen to minimize impact on any underlying disease state.

The primary variable will be respiratory rate and minute ventilation, based on the hypothesis of affecting adenosine receptors and preclinical observations. Cardiopulmonary exercise testing is included because provocation of the system may elicit measurable changes in physiological parameters that are not otherwise observed. Exercise testing also provides an opportunity to simulate the conditions that could contribute to dyspnea during daily activities.

A loading dose of 450 mg is chosen to maximize the potential of eliciting dyspnea. This dose will establish safety margins for a clinical loading dose that may be up to 270 mg. Dosing to 3 days will allow for attainment of steady-state plasma concentrations. Again, this will provide for assessment of dyspnea under clinically relevant conditions. A placebo crossover will be performed because dyspnea is a highly subjective sensation, and therefore comparison to a placebo baseline is desirable.

A retrospective genetic analysis to explore the genetic variables in genes that are important to absorption and disposition of, and response to AZD6140 may be carried out. Genetic sampling will be optional to all subjects enrolled. Subjects will receive the same treatment and care in the main study whether or not subjects donate a blood sample for genetic research. The genetic data from this study may be pooled with genetic results from other studies on AZD6140 to generate hypotheses to be tested in future studies.

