3.3.2 Inclusion criteria

For inclusion in the study subjects must fulfill all of the following criteria:

1. Give written informed consent and agree to comply with all requirements of the study;
2. Generally healthy male or female ages 55 to 75 years, inclusive; within the following 3 cohorts:

Cohort	Volunteer Type	Respiratory criteria
A	Healthy	N/A
B	Mild Asthmatic	Clinical diagnosis > 1 year; FEV ₁ ≥ 70% predicted; no exacerbation in past 8 weeks; reversibility demonstrated within the past year (≥ 12% or 200 mL)
C	Mild COPD	Clinical diagnosis > 1 year; FEV ₁ ≥ 60% predicted; no exacerbation in past 8 weeks; FEV ₁ /FVC ratio < 70%; history of tobacco smoking > 10 pack year

3. Weight at least 50 kg and have a BMI between 18 to 30 kg/m² inclusive unless approved by the sponsor and investigator. (BMI will be calculated as weight in kg/height in m² and will not be reported on the case report form.);
4. Females must be post-menopausal (cessation of regular menses for 12 months) or surgically sterile;
5. Have normal physical examination, laboratory values and vital signs, unless the investigator considers an abnormality to not be clinically significant or a symptom of mild COPD or mild asthma (Cohort B and Cohort C patients);
6. Subjects are able to communicate with the investigator, and to understand and comply with all study requirements.

For inclusion in the genetic component of the study, subjects must fulfill the following criteria:

1. Provision of informed consent for genetic sampling and analyses

If a subject declines to participate in the genetic component of the study, there will be no penalty or loss of benefit to the subject. The subject will not be excluded from other aspects of the study described in this Clinical Study Protocol, so long as they consent.

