6.4.3.1 Pharmacodynamic

The respiratory parameters will be descriptively summarized by treatment and listed by individual at each time point by treatment and visit for each of the cohorts using descriptive statistics. These will also be supported with graphical displays in order to ease making comparisons.

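### The patient cohorts are there to show whether response to AZD6140 differs from healthy volunteers, but neither the objective nor the planned summaries contrast the AZD6140-minus-placebo response between cohorts

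*Protocol*

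**What the plan says.** Section 1.2 includes the patients "to assess whether the sensitivity of patients with respiratory disease is greater than in healthy volunteers". Section 3.2 repeats the reason: "Asthma and COPD patients are included primarily to ascertain if the physiologic response differs from healthy volunteers". Both sentences describe a difference between cohorts in what the drug does.

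The corresponding objective in section 2.2 is to "Compare respiratory parameters between the healthy volunteers, mild asthma patients, or COPD patients". It mentions neither the drug nor placebo.

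For the analysis, section 6.4.3.1 has the respiratory parameters "descriptively summarized by treatment and listed by individual at each time point by treatment and visit for each of the cohorts", with supporting graphs. The synopsis (Statistical methods) and section 6.1.2 add changes from baseline within each period. Section 6.4.3 says that no formal analysis of the pharmacodynamic data will be done. Section 6.4.3.3 allows, but does not require, regression slopes on concentration with 95% confidence intervals.

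Section 6.4.2.1 limits the pharmacodynamic set to subjects with evaluable measurements in both periods. Section 3.2 gives comparison with placebo as the reason for the crossover.

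**The concern.** The question behind the three cohorts is a cohort-by-treatment question. It is answered by taking each subject's AZD6140-minus-placebo difference and comparing it between cohorts. The crossover collects the data for this, but the protocol never forms the quantity. The reader is left to combine four cell summaries per cohort pair (two treatments, two cohorts) by eye, with no measure of uncertainty for the result.

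The objective as worded is also a different comparison. Cohorts are selected on respiratory measurements: Cohort C requires "FEV ₁ /FVC ratio < 70%; history of tobacco smoking > 10 pack year", Cohort B requires an FEV1 floor and documented reversibility, and Cohort A has no respiratory criterion. A comparison of the parameters themselves therefore mixes disease with drug response, at least for spirometry.

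Section 3.2 wants the patient data to inform later clinical studies. If similar-looking panels from cohorts of 8 were taken to mean that patients are no more sensitive, that inference would rest on no stated precision.

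**Working it through.** **The plan's own figure.** Three cohorts of 8 give 3 × 8 = 24, as the synopsis states. Section 6.4.4 says the size was not based on power, and no SD, effect size or alpha is given, so there is nothing further to reproduce.

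**What each summary estimates.** Let cohort c have pre-dose level m_c, drug effect e_c and change over a period without drug p_c (placebo response, repeated testing, time of day). The target is e_C − e_A.
- On-drug level, C minus A: (m_C − m_A) + (e_C − e_A) + (p_C − p_A).
- On-drug change from baseline: (e_C − e_A) + (p_C − p_A).
- AZD6140-minus-placebo difference in change from baseline: e_C − e_A. A period effect cancels when the two sequences carry equal weight.

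The planned changes from baseline thus remove the level gap. Removing p needs the placebo period, which is summarised separately but never subtracted within subject.

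**Illustration by simulation.** All values are assumptions: 8 per cohort, between-subject SD 1, within-subject SD 0.5, drug effect 0.5 in the healthy cohort, and no placebo or period effect (p = 0).

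| Pre-dose gap | True response difference | On-drug level | Change from baseline | AZD6140 minus placebo |
|---|---|---|---|---|
| 1 | 0 | 1.0 | 0.0 | 0.0 |
| −0.7 | 0.7 | 0.0 | 0.7 | 0.7 |

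Comparing levels can create a difference or hide one. Change from baseline does neither when p = 0.

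**Precision of the missing contrast.** Let SD_d be the SD of the within-subject AZD6140-minus-placebo difference, assumed equal across cohorts. The protocol gives no SD, so results are in SD_d units. Section 3.1 allows up to 12 randomised per cohort to secure at least 8 completers, so 12 is an upper bound.

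Half-width = t(0.975, df) × SD_d × √(2/n).
- n = 8, two cohorts, 14 df: 2.145 × √(2/8) = 2.145 × 0.5 = 1.07 SD_d.
- n = 8, error pooled over three cohorts, 21 df: 2.080 × 0.5 = 1.04 SD_d. With sequence fitted within cohort (18 df) it is 1.05 SD_d.
- n = 12, two cohorts, 22 df: 2.074 × √(2/12) = 2.074 × 0.408 = 0.85 SD_d. Pooled over three cohorts (33 df) it is 0.83 SD_d.

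For comparison, the effect within one cohort of 8 has half-width 2.365/√8 = 0.84 SD_d.

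**The case against.** The strongest reply is that the plan is better than the objective's wording suggests. Changes from baseline by treatment, visit and cohort are planned, so a reader might infer that the cohort question will be settled from raw levels, and the documents do not support that. The level gap affects the objective's wording and the tables of raw values, not every table. It is also certain only for spirometry: no entry criterion separates the cohorts on respiratory rate or minute ventilation.

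A reader might likewise make much of the dosing order ("All healthy volunteers (Cohort A) will be dosed and evaluated initially"). But this is a single-centre study expected to run from October to December 2004, and nothing in the protocol points to drift over time. An additive drift between cohorts would in any case drop out of the within-subject difference.

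The objective can be read as shorthand for response, since sections 1.2, 3.2 and 6.4.1 give its purpose. The concentration-response plots by cohort also bear on sensitivity. Both points have some force, but the slopes are optional and no comparison of them between cohorts is stated.

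Finally, the study is exploratory and a statistical analysis plan is promised. That fully answers any complaint about missing power or tests, and none is made here. It does not answer this point: the protocol itself words the objective, describes the analysis and excludes formal analysis. A later plan could add the contrast, but it would sit awkwardly with the exclusion in section 6.4.3. The protocol nowhere says that it will conclude there is no greater sensitivity; the risk lies in how the summaries are read.

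**Conclusion.** The point holds as a mismatch between the reason for the cohorts and what is compared. The rationale asks about response to AZD6140; the objective compares parameters; and the stated analysis stops at separate summaries, without a within-subject AZD6140-minus-placebo difference, a between-cohort contrast or an interval for one.

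Its size is about 1.0 to 1.1 SD_d either side of the estimate with 8 per cohort, and about 0.85 SD_d with 12. When the estimated contrast is near zero, cohort differences of that order cannot be ruled out. These figures assume equal SDs across cohorts, roughly normal differences and, where sequence is fitted, balanced sequences. They cannot be put in breaths or litres per minute without an SD.

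A reader might also infer that the lack of an all-cohort average is a defect, because the primary objective names no cohort. Sections 3.2 and 6.4.1 frame the effect by population, so that average is optional.

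**What to change.** 1. Section 2.2 and the synopsis: reword the objective as comparing the AZD6140-minus-placebo response between cohorts.
2. Section 6.4.3.1: add, by cohort, the within-subject AZD6140-minus-placebo difference in change from baseline for respiratory rate and minute ventilation, and descriptively for spirometry and the two dyspnea scales.
3. Same section: for the continuous variables, add the asthma-minus-healthy and COPD-minus-healthy differences in that quantity, with exploratory 95% intervals and no test.
4. Section 6.4.3: state that these estimates and intervals are permitted despite the exclusion of formal analysis. Section 6.4.3.3 already contemplates 95% intervals.
5. Require the report to state the width of the cohort contrast and that differences of that order are not ruled out when the estimate is near zero.

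No new data or procedures are needed, because the pharmacodynamic set already requires both periods. The cost is a few table rows and a less definite statement about the cohorts. A mean across all cohorts may be added but is not needed.
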